Inflammation has been shown to be part of the early pathogenic mechanism of AD¹ and PD², and represents an important potential target for therapy. These two diseases have distinct patterns of cognitive dysfunction, especially early in the disease course. In AD, amyloid depositions occur early in the disease process and by the time clinical symptoms are evident, are diffuse in the brain, while the spread of tau pathology in the brain occurs in a predictable topography, with spread from the medial temporal regions early in the disease to the association cortices of the frontal and parietal lobes as the disease progresses. This topographical distribution is closely associated with specific cognitive changes, which can be tracked with neuropsychological tests. The spread of disease-specific proteins in PD is less well understood, but there are particular cognitive trajectories that can be followed. Inflammation has also been shown to play a role in these disorders. If inflammation is a common element which can be visualized and quantified regionally, and is associated with particular cognitive dysfunction, then this would (a) demonstrate a target of therapy which may not be disease specific and (b) identify a way to measure the impact of any intervention.

Microglia are the central nervous system's phagocytes, and are distributed throughout the brain. They are very active and, in addition to an anti-inflammatory role, they have a role in plasticity and remodeling of synapses³. GE180 is an experimental PET tracer that binds to a mitochondrial translocator protein (TSPO), which is produced by microglia and is a putative biomarker for inflammation. TSPO is minimally expressed in the CNS in humans when healthy, but dramatic increases are apparent in response to neuronal damage and inflammation⁴. There have been some human studies with GE180 already⁵ and it is similar to an earlier experimental tracer ¹¹C-(R)-PK11195 which has been tested more exhaustively over the last 20 years⁶. GE180 has been found to be superior to ¹¹C-(R)-PK11195 due to stronger signal to noise ratio and different pharmacokinetic properties including longer half-life⁷. Animal studies have shown GE180 to detect both AD-related and age-related changes in mice⁸. Several studies are currently underway in the UK, Canada and the USA using GE180 in disorders including AD and PD. To our knowledge, none of these studies uses as in depth cognitive profiling as will be used in the current study.

Early research with a more primitive PET tracer ¹¹C-(R)-PK11195 revealed that AD patterns of inflammation were suggestive of regional change and associated with reduced cognition as assessed using a nonspecific measure⁹. In PD, two different patterns emerged, one being more general, the other more specific to certain cortical regions. This early research did not take advantage of neuropsychological methods which might elucidate the specific cognitive change

Title: The Relationship between Neuropsychological Testing and MRI, PET and Blood Biomarkers in Neurodegenerative Disease (NIH): AIM 2

Co-PIs: [name] and [name]

seen in these two diseases. By applying these methods, we hope to gain a far deeper understanding of the relationship between microglial activation and cognition across these two diseases.

1.1 Purpose

The purpose of the study is to assess the relationship between (a) overall and (b) regional inflammation with (a) overall and (b) domain-specific cognitive function in AD and PD. If we demonstrate a correlation between regional uptake of GE180 and specific cognitive profiles, further research will be warranted to investigate whether therapeutically driven reduction in inflammation also leads to improvement in cognition.

2. Study Objectives

The overall objective is to establish the relationship between regional microglial activation and neuropsychology test scores in patients with diagnoses of Alzheimer's disease and Parkinson's disease.

We will test the hypothesis that regional enhancements in microglial activation would be reflected in neuropsychological test scores: The degree of memory impairment would be related to medial temporal lobe microglial activation, visuospatial impairment would relate to more posterior activation, executive dysfunction would relate to frontal activation. We will also test the hypothesis that higher levels of global inflammation will be associated with more severe cognitive impairment, especially in patients with mild cognitive impairment.

3. Study Design

This study will involve a cohort that is currently being established at the Cleveland Clinic Lou Ruvo Center for Brain Health. The cohort has been established under the NIH Center of Biomedical Research Excellence (COBRE) grant and involves annual collection of detailed neuropsychological and biomarkers (blood and neuroimaging) from all participants annually. Data are filed in a registry (CNTN). Under a data sharing agreement, all neuropsychological, blood screening, MRI, and PET data from CNTN will be available to [name] (who is also a Clinical Core Leader on the COBRE project). Participants include healthy participants, participants with PD (with and without mild cognitive impairment (MCI)) and patients with MCI (with or without positive florbetapir scan, which demonstrates underlying AD changes likely causing the cognitive impairment) and patients with AD. For the current study, we will focus on patients with MCI with associated underlying AD or PD.

Participants will undergo GE180 PET. Our approach to PET data collection and analysis will be similar to work done previously with an earlier generation ligand ¹⁰ and to other work with this tracer⁵. We will complete ECGs prior to and immediately following injections. Briefly, the ligand will be injected, scan acquisition will then begin and will be collected in list mode and rebinned into 18 time frames post acquisition.

Title: The Relationship between Neuropsychological Testing and MRI, PET and Blood Biomarkers in Neurodegenerative Disease (NIH): AIM 2

Co-PIs: [name] and [name]

The total duration of the study will be around 2 hours, and the participants will receive \$50 compensation for the visit.

4. Population

A total of 70 participants will be recruited from the CNTN cohort. Specifically, we will recruit 10 healthy participants, 20 MCI (10 of whom will be florbetapir positive, and 10 florbetapir negative), 20 AD patients and 20 PD patients, 10 of whom will be cognitively intact and the other 10 will meet criteria for MCI. Participants will be age matched and they will be extracted from the larger CNTN cohort which stratifies to race based on the Nevada data from the 2014 US Census.

4.1. Inclusion/Exclusion criteria

Inclusion criteria

1. Be enrolled in CNTN
2. Aged 55 to 90
3. Available study partners
4. For MCI patients, fit criteria based in Movement Disorders Task Force or NIA

Exclusion criteria

1. Significant neurological disorders other than AD or PD;
2. Unstable medical conditions
3. History of major psychiatric diseases
4. MRI evidence of infarction or other focal lesion or multiple lacunes
5. Clinically significant abnormalities in B12 or TSH
6. Identified as having a common polymorphism (rs6971) in the TSPO gene which has been shown to reduce binding affinity of tracers similar to GE180¹¹. This testing will be done as part of their CNTN participation.

In addition, subjects must answer questions in regards to their history of radiation exposure over the past year (past 12 months to day of screening). If their radiation exceeds half of the recommended amount (any amount greater than 25 mSv), they may not participate at the present time. However, assuming they are eligible against all other inclusion/exclusion criteria, they may be eligible for a scan in the future once their 12 month exposure is less than half of the recommended amount.

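### The 12-month radiation total is sourced only from the participant's own answers, although 50 of 70 are recruited into cognitively impaired groups and two ready checks go unassigned

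*Combined protocol and SAP*

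**What the plan says.** Section 4.1 (Inclusion/Exclusion criteria) follows its numbered criteria with a radiation rule: "subjects must answer questions in regards to their history of radiation exposure over the past year". The window is the 12 months up to screening. The consequence is: "If their radiation exceeds half of the recommended amount (any amount greater than 25 mSv), they may not participate at the present time". Someone over the limit may be scanned later, once the 12-month figure has fallen.

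Section 4 (Population) sets the groups. "A total of 70 participants will be recruited from the CNTN cohort", made up of "10 healthy participants, 20 MCI (10 of whom will be florbetapir positive, and 10 florbetapir negative), 20 AD patients and 20 PD patients". The PD group is split evenly between cognitively intact participants and those meeting MCI criteria.

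Two other provisions bear on the point. Section 3 (Study Design) says that, under a data sharing agreement, "all neuropsychological, blood screening, MRI, and PET data from CNTN will be available" to a study lead. Inclusion criterion 3 in section 4.1 is "Available study partners". The Consent Visit text under section 5 has the partner review the materials with the participant and sign consent as well. Neither provision is linked to the radiation rule. Section 4.3 (Subject screening) does not mention radiation.

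**The concern.** The rule depends on recalling a year of imaging, and most of those asked are enrolled on a diagnosis of impaired cognition. Memory impairment is one of the deficits in the study's own hypotheses (section 2). A scan that is forgotten is left out of the total, so this kind of error moves a person towards passing. What is at stake is participant protection: someone above the protocol's own limit could be injected and scanned. No endpoint or analysis is affected.

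Some of the relevant exposure can be foreseen. CNTN collects neuroimaging annually (section 3), and participants are recruited at CNTN follow-up visits with amyloid PET already done (Recruitment at CNTN Study Visit, under section 5). A CNTN PET could therefore fall inside the 12-month window, and the study need not rely on memory to know about it.

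**Working it through.** **1. Reproduce the total.** Inputs are the group sizes in section 4: 10 healthy, 10 florbetapir-positive MCI, 10 florbetapir-negative MCI, 20 AD, 10 PD cognitively intact, 10 PD-MCI.

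10 + 10 + 10 + 20 + 10 + 10 = 70, which matches the stated total.

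**2. Share in impaired groups.** MCI 20 + AD 20 + PD-MCI 10 = 50, and 50/70 = 71.4%. The other 20 are the 10 healthy and 10 cognitively intact PD participants.

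**3. What an omission does to the rule.** Only totals greater than 25 mSv bar entry, so a recorded 25 passes. If the true total is T > 25 mSv and the only error is omission, the person passes when the omitted exposure is at least T − 25, a share 1 − 25/T of the total. The values of T below are assumptions that show the shape; the documents give no distribution of exposure. The last row is the full recommended amount implied by section 4.1 (25/0.5 = 50 mSv).

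| Assumed true total (mSv) | Omission needed to pass (mSv) | Share of total |
|---|---|---|
| 30 | 5 | 17% |
| 40 | 15 | 38% |
| 50 | 25 | 50% |

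Scans are discrete and differ in dose, so the shares are not recall rates. Without mSv values for the CNTN PET, the GE180 PET/CT or outside imaging, and without a recall-error rate, no expected number of misclassified participants follows.

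**4. What each available source can cover.**

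- CNTN PET data (section 3): CNTN's own PET scans, and any CT acquired with them. The CNTN MRI data are irrelevant because MRI gives no ionising dose.
- Study partner (section 4.1, criterion 3; Consent Visit): can prompt recall of CT or nuclear medicine studies done elsewhere, which the CNTN record cannot show.
- The protocol already works this way for another criterion. Section 4.3 takes TSPO rs6971 status from CNTN data held before recruitment.

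**The case against.** The strongest reply is that this argues from silence. Section 4.1 requires subjects to answer questions; it does not say that their answers are the only evidence, or that the partner or the CNTN record is excluded. Such detail often sits in a screening form. Section 9.2 says the CRFs have been constructed, and a monitoring plan is described as attached; neither is in the documents. CNTN staff also put forward suitable participants, and the recipient of the CNTN data holds a lead role in that project, so the team may well know of recent CNTN scans. This stands: the gap is an unstated check, not a conflict within the protocol. It does not remove the case for naming the sources, since no section says that either is consulted for this limit.

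Several stronger readings are tempting but unsupported:

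- A reader might infer that 71% of the sample cannot report reliably. The figure counts diagnoses. Section 2 names visuospatial and executive deficits as well as memory, so an MCI or PD-MCI label need not mean poor recall.
- A reader might infer that recall error always favours entry. That is true only of omissions. Misdating an older scan into the window raises the total.
- A reader might infer that CNTN data settle the question. They cover only CNTN's own scans.
- A reader might infer that a complete check needs outside medical records. Retrieving these could require extra authorisation and is not a few-minute task, so the point does not depend on it.

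**Conclusion.** The point holds as a cheap improvement. The only source the protocol names for the 12-month total is the participant's own answers, and 50 of 70 participants (71%) are recruited into groups defined by cognitive impairment. That count is exact. The direction of the risk is established only for omitted scans, and its size is unknown: the documents provide neither recall-error rates nor doses per scan. They do not show that anyone would be wrongly admitted, nor that the protocol rules out other sources. The conclusion assumes that no unseen screening form already names these checks; if one does, section 4.1 need only say so. No view is taken on the limit itself.

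**What to change.** In section 4.1, after the sentence on the exposure questions, state two things:

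1. CNTN PET scans within the 12 months before screening, with any associated CT, are taken from the CNTN record already shared with the study. The documents do not list the shared fields, so confirm that scan dates are among them.
2. The exposure questions are put to the participant together with the study partner.

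The limit and the provision for later participation are unchanged, and outside medical records need not be retrieved.

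The cost is a wording change in the protocol and screening form and a few minutes of coordinator time per participant. No new visit is needed, since the partner already takes part in consent. A few more people may be found over the limit and deferred, which section 4.1 already provides for.

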4.2 Subject recruitment

All participants will be recruited via the CNTN cohort.

4.3 Subject screening

All subjects who are part of the CNTN will be eligible for participation in the current study, other than those carrying a known genetic polymorphism, TSPO rs6971 polymorphism which impacts binding of GE180 and other TSPO binding agents, which occurs in approximately 10% of the

Title: The Relationship between Neuropsychological Testing and MRI, PET and Blood Biomarkers in Neurodegenerative Disease (NIH): AIM 2

Co-PIs: [name] and [name]

population. We will not recruit patients with this polymorphism. Since they will have already been followed in CNTN we will have this data prior to recruitment.

5. Study Procedures

The below procedures will be completed on all participants:

4.1 Recruitment at CNTN Study Visit

The CNTN has been collecting data since mid-2016. We will recruit participants as they come for their follow-up visit. Suitable participants will be made available for the study by the CNTN staff if they agree for data to be shared with this study. At that point, study staff will contact the potential participant and conduct a brief screen over the telephone or in person, explaining the content of the current sub-study. If the potential participant demonstrates interest and willingness to continue, they will be asked to come in to discuss informed consent at their next CNTN visit. We will recruit patients into each cohort from the CNTN, at which point they will already have been characterized with neurology, neuropsychology and neuroimaging (amyloid PET and MRI) as well as having blood work completed. CNTN participants will be invited to recruit in the current study at their CNTN visit.

4.2 Consent Visit

This could potentially happen on the same day as the CNTN visit, in order to reduce the number of study visits. Participants will be given time to review the materials with their study partner, and then with the coordinator who will allow them to ask any questions they may have. Once fully informed written consent is obtained by both the patient and their study partner, the baseline GE180 PET visit will be scheduled.

4.3 PET

The participants will come for their visit, have their vitals and ECG taken, and will have fresh blood samples drawn. GE180 will then be injected and the scan will be performed. They will then have a secondary ECG. After this they will be free to leave. They will receive a wellness phone call from the study coordinator 48-72 hours later. The coordinator will stop making attempts to reach the participant after three unanswered calls.

6. Data analysis

Study size determination was completed using another previously published study ¹² that used an earlier generation microglial ligand. Based on binding potentials in the same region (anterior cingulate cortex) we calculated that at a significance level of .05, and in order to attain a correlation of $r=.8$ we would require 10 subjects for 90% power in analyses of microglial activation from each of the regions of interest and the key cognitive outcome measures. Given that we are using a different ligand and will be looking at more regions, we have increased the number so we can be confident in our results. It is important to note that sample size calculations based on neuroimaging

Title: The Relationship between Neuropsychological Testing and MRI, PET and Blood Biomarkers in Neurodegenerative Disease (NIH): AIM 2

Co-PIs: [name] and [name]

data are limited, but the numbers proposed here are similar to or in excess of other studies using and novel PET ligands ¹⁰, thus we predict that the group sizes will be sufficient.

Data Analysis will be conducted by the study team under the direction of the Principal Investigator.

Image analysis will be conducted using parametric analytic technique in SPM12, combining GE180 results with the participants' own MRIs. This will allow us to compare individuals in each disease group with an averaged image of controls. In addition, we will be able to extract uptake values in regions of interest to compare across groups and in relation to test scores. This approach is being used by colleagues at another site that is currently studying GE180 in older adults.

Microglial activation data from each of the region of interest (ROI), in addition to overall cortical load, will be extracted. It will be represented statistically as a function of cortical thickness in that region. These data will be used in two analytic steps: the first using measures of overall cognitive function (assessed with the Dementia Rating Scale (DRS) and Montreal Cognitive Assessment (MoCA)), and the second using key cognitive outcome measures specific to the domains of memory, visuospatial function, language and executive functioning. These measures are all collected as part of the CNTN. We will use a linear regression model to assess whether regional microglial activation predicts cognitive performance. We will also complete repeated measures analyses to assess whether there is a change in microglial activation between time points and, if so, if this relates to changes in the cognitive measures.

6.1 Predicted outcome: At baseline, we expect to find overall cortical load of GE180 uptake to predict summary scores on the DRS and MoCA, and for regional loads to predict specific cognitive domains. In PD-MCI we expect more cortical enhancement than in the PD-NCI subjects. Specific expectations across disease states include that hippocampal and temporal cortex load will be related to memory, frontal cortex load to executive ability, parietal load to visuospatial ability. We also expect baseline levels of microglia to predict future decline in cognition but there will not be an increase in microglial activation over time. This final expectation is based on data collected with the earlier generation microglial ligands, but change over time is yet to be explored in humans with GE180.

7. Study Drug

7.1 Investigational Agent

GE180 is a PET imaging agent which was developed as a non-invasive *in vivo* probe of neuroinflammation. The mechanism of action is based on its high affinity for TSPO and high selectivity, with little binding to other receptors, transporters and channels. TSPO is elevated in response to neuronal damage and inflammation, such as occurs in neurodegenerative disease. *In vitro* studies support GE180's high affinity to TSPO and high selectivity, with little binding to other receptors, transporters and channels.

7.2 Preclinical data

Nonclinical pharmacology data of GE180 supports its potential use to visualize TSPO *in vivo*. In preclinical models of stroke and inflammation, GE180 has been shown to be effective in detecting

Title: The Relationship between Neuropsychological Testing and MRI, PET and Blood Biomarkers in Neurodegenerative Disease (NIH): AIM 2

Co-PIs: [name] and [name]

inflammation in animal brains^{7,13}. Specifically, in mouse models of normal aging and AD, Liu and colleagues found a clear association between GE180 uptake and amyloid plaques, as well as immunohistochemical co-localization of GE180 and other microglia markers. They also showed an age-dependent elevation in whole brain uptake consistent with the notion that both aging and AD pathogenesis involve increased inflammation⁸.

7.3 Clinical data to date

Human studies of early inflammatory markers were hampered by reduced binding affinity¹⁴ and difficulty distinguishing the signal from noise related to uptake in the endothelial cells of the blood brain barrier and venous signal¹⁵. It was hoped that GE180 would counteract these problems and enhance the visualization of neuroinflammation in humans. Several clinical studies are currently underway. The first publication of human research has been focused on methodology⁵. Fan et al used 15 healthy adults aged 50-85 years. Their study was used to optimize scan length and to investigate the feasibility of generating parametric maps using graphical analysis. Results from their study have been incorporated into the design of the current study.

7.4 Dose rationale

GE180 is an intravenously administered diagnostic radiopharmaceutical used for PET. It is formulated as a clear, colorless aqueous solution containing NMT 10.0% v/v ethanol in phosphate buffered saline (PBS) with a pH of 6 – 8. It contains 90 – 110% of the labelled amount of ¹⁸F expressed as MBq/mL. There are no preservatives. It is manufactured to GMP standards and is supplied in a sterile endotoxin-free 10 mL glass vial. Study participants will receive a standard dose of 185MBq with maximum radioactivity dose of 270 MBq in a maximum volume of 10 mL (bolus) of GE180, containing not more than 2 µg/mL GEH120714 (20 µg for a 10 mL dose). This is consistent with other sites using the tracer.

Title: The Relationship between Neuropsychological Testing and MRI, PET and Blood Biomarkers in Neurodegenerative Disease (NIH): AIM 2

Co-PIs: [name] and [name]

